While the world waits for an effective and safe vaccine, according to experts in the field, the pandemic is likely to rage on for another 12 months or longer. For these sectors to survive (in the short-term), COVID-19 mitigation strategies are urgently needed. The current strategy that is used in many airports is to require airlines to conduct a health check of travellers before they board a flight and to check their body temperature at ticketing areas or boarding gates.

However, this strategy is not very effective because these measures are relatively insensitive (only a minority of COVID-19 patients have raised temperature at any given point in time during their disease course) and thus unlikely to identify individuals with SARS-CoV2, who are minimally symptomatic or completely asymptomatic at the time of travel. Indeed, public health experts have poignantly stated that transmission of the virus through asymptomatic individuals is the “Achilles’ Heel of Current Strategies to Control COVID-19”.⁴ This is because, unlike SARS-CoV1, the cause of the original SARS epidemic in 2003, SARS-CoV2 sheds at high concentrations from the nasal cavity even in asymptomatic individuals, who may harbor the virus but have yet to demonstrate any symptoms during the prodromal phase of the disease.⁵ Even with masking and social distancing, such individuals would be at a high risk of spreading the virus during air travel, especially during long flights.⁶ One approach to reducing the risk of SARS-CoV2 transmission during flights is to “screen” for those travelers who are likely to harbor the virus (even though they may have no or minimal symptoms) at airports across the country. However, the current diagnostic approach, which uses real-time reverse transcriptase polymerase chain reaction (RT-PCR) to detect the presence of viral RNA from nasopharyngeal swabs, cannot be easily deployed for this purpose

As it is expensive (>\$100/test), time-consuming (with turnaround times of 1-2 days) and requires trained health care personnel to administer the test. A potential solution to this conundrum is to use a “point-of-care” test, which can be deployed at airports and whose results will be available within 1 hour of testing.⁷⁻⁹ However, for these assays or platforms to be viable, they will need to be used as “screening” rather than “diagnostic” tests (see below for more detailed discussion on this topic), and be relatively simple to use (so ideally they can be self-administered) and inexpensive.

What is the difference between diagnostic and screening tests?

Diagnostic testing for SARS-CoV-2 is intended to identify occurrence at the individual level and is performed when there is a reason to suspect that an individual may be infected, such as having symptoms or suspected recent exposure, or to determine resolution of infection. Examples of diagnostic testing include testing symptomatic individuals who present to their healthcare provider, testing individuals through contact tracing efforts, testing individuals who indicate that they were exposed to someone with a confirmed or suspected case of coronavirus disease 2019 (COVID-19), and testing individuals present at an event where an attendee was later confirmed to have COVID-19. The U.S. Food and Drug Administration’s (FDA) [FAQs on Testing for SARS-CoV-2](#) also address diagnostic testing for SARSCoV-2. Screening tests for SARS-CoV-2, on the other hand, are intended to identify occurrence at the individual level even if there is no reason to suspect infection—e.g., there is no known exposure. This includes, but is not limited to, screening of non-symptomatic individuals without known exposure with the intent of making decisions based on the test results. Screening tests are intended to identify infected individuals without, or prior to development of, symptoms who may be contagious so that measures can be taken to prevent further transmission. Examples of screening include testing plans developed by a workplace to test its employees, and testing plans developed by a school to test its students, faculty, and staff. In both examples, the intent is to use the screening testing results to determine who may return and the protective measures that will be taken. FDA’s [FAQs on Testing for SARSCoV- 2](#) also address screening testing for SARS-CoV-2. In sum, a screening COVID-19 test is one that is specific for SARS-CoV2 but has a lower sensitivity (i.e. ability to pick up the virus) than that of a diagnostic test. Thus, even those who have a negative screening test should be considered potentially infectious and must adhere to social distancing and masking rules as per all the other passengers on the plane. Those who are tested positive on the screening test must be assumed to have COVID-19 until proven otherwise by a confirmatory RT-PCR test (which is the gold standard). This approach of using “point-of-care” screening tests was recently advocated by The New England Journal of Medicine.¹⁰

Primary Objective

The primary objective of this pilot study is to determine the feasibility and effectiveness of a COVID-19 screening program for passengers departing from YVR. This research study is conducted by The University of British Columbia (UBC) and Providence Health Care, sponsored by WestJet and Vancouver Airport Authority. The experimental study investigates point-of-care rapid test device for detecting SARS-CoV-2, the virus responsible for COVID-19. The study is investigating a method of rapid-testing for COVID-19 and will help inform the safest and most efficient way of testing departing passengers prior to security screening at Vancouver International Airport (YVR). This study is also evaluating a new passenger management system.

Summary of the Research Proposal

Purpose:

The purpose of this pilot study is to determine the feasibility and effectiveness of a COVID-19 screening program at YVR for WestJet and KLM passengers.

Hypothesis:

SARS-CoV-2 infection can be effectively screened using point-of-care rapid antigen assays.

Justification:

Passengers are required to wear masks and physically distance while traveling by air. However, the majority of general public is still worried about the potential risk of contracting COVID-19 on airplanes, especially during long flights. We need to develop methods and strategies to quickly screen for SARS-CoV-2 infection, prior to boarding flights.

Objectives:

1. To develop and deploy a management algorithm for COVID-19 screening at YVR that will involve the use of point-of-care rapid test device.
2. To evaluate the acceptability of such screening algorithm and determine the costs of deploying the program.

Research Design:

Study Population: Working in collaboration with WestJet and KLM we will invite all passengers meeting Inclusion/Exclusion on outbound flights from YVR Airport to participate in this study.

Phase 1: We will work with YVR and WestJet to enroll 200 subjects into the study. For this initial phase we are looking to determine the rate of positivity in the cohort. This initial phase is needed to evaluate the feasibility of this pilot program and to refine the initial management algorithm. Health Canada-approved Panbio Covid-19 Ag Rapid Test Device by Abbott Rapid Diagnostics (approved for Lab-based test and Point of care test on 2020-10-05) will be used in Phase 1.

Phase 2: Strategies for achieving higher-throughput will be determined after completion of Phase 1. In phase 2, we will continue to work with YVR and WestJet, with the addition of KLM, to enroll 700 subjects into the study. Phase 2 will further assess the efficiency of our COVID-19 screening and passenger management algorithm.

The study is purposefully designed to be as minimally invasive to the passengers' travel plan as possible. The Study Plans for Phase 1 and Phase 2 are detailed below.

Statistical Analysis:

- When we aggregate the data for analysis, we will use basic statistics to determine mean, variance, standard deviation, and positivity rate...etc.

INVESTIGATIONAL PLAN

Phase 1 Recruitment

Inclusion Criteria:

1. The subject must be between 19 and 80 years of age.
2. The subject must be a resident of B.C.
3. The subject must have a ticket to board a WestJet flight departing from Vancouver International Airport (YVR).
4. Have a minimum of 75 minutes of free time prior to the scheduled flight's departure.

Exclusion Criteria:

1. We will exclude subjects who have previously tested positive for COVID-19 within the past 90 days
2. We will exclude subjects who cannot provide written informed consent

Phase 2 Recruitment

Inclusion Criteria:

1. Subject has access to accommodation in Canada for safe-isolation as per public health guidelines
2. Between the ages of 13 – 90
3. Travelling on any WestJet or KLM flight
4. Have a minimum of 70 minutes (if travelling within Canada) or 90 minutes (if travelling International) of free time prior to the schedule flight's departure

Exclusion Criteria:

1. We will exclude subjects who have previously tested positive for COVID-19 within the past 90 days
2. We will exclude subjects who cannot provide written informed consent or assent

Onsite Recruitment

For Phase 1, we will approach eligible passengers arriving at YVR terminal between 8 AM and 12 PM noon. For Phase 2, we will approach eligible passengers arriving at YVR terminal between 6:30 AM and 10:30 AM to capture WestJet's largest carrier departing at 9 AM, and between 11:30 AM and 3:30 PM on Thursday and Sunday for KLM flights. We will also mention a discount coupon will be given to WestJet passengers who successfully complete the study.

a) Passengers will purchase tickets directly from WestJet or KLM. On the day of departure, passengers will make their way to the check-in kiosk where they will go through the normal protocol of checking their bags. The airline staff will ensure that the passenger has minimum free time prior to their flight. If that is the case the staff member will inform them of Optional study conducted by UBC, WestJet, KLM and YVR - looking into the feasibility of a COVID-19 point-of-care rapid test device and algorithm for passenger management.

b) If the Passenger is interested, they will be directed to the Welcome Booth where they will meet a Study Coordinator and/or YVR staff. The Study Coordinator will provide each passenger with a welcome package consisting of 1) Simple study info sheet covering the purpose, the study plan, inclusion exclusion and potentiality of missing their flight if they participate; 2) A brochure with high-level details and frequently asked questions (see "General Brochure" in accompanying collateral document) 3) A water bottle; and 4) A pen which they will use for filling out the informed consent form and study questionnaire.

c) All passengers meeting the inclusion/exclusion criteria will be approached after checking bags. We will ensure that passengers have minimum required time prior to flight departure. If the subject is interested, they will be escorted to Informed Consent Area or the Citizen Care Pod for the full run through of the Informed Consent Form. After informed consent, we will start the process of sample collection.

Advance Recruitment

For WestJet passengers only, we will also recruit by sending an email at 72 hours pre-departure to WestJet guests who are flying out of Vancouver (see “WestJet Email to Guests”). The email will point to a WestJet microsite with further information on the study (see “WestJet Microsite”) and interested participants will be able to register in advance for the study at testingyvr.ca (see “Sign-up Microsite”). Those who choose to sign up in advance will receive a series of confirmation emails (see “Confirmation Emails”). Those signing up in advance must meet all the eligibility criteria and will follow the steps outlined above.

Details of Study Procedures

The study is purposefully designed to be as minimally invasive to the passengers’ travel plan as possible. The General Study Plan is detailed below.

Welcome Booth

- Study Coordinator stationed here with YVR staff (all wearing masks and are able to maintain appropriate distance)
- Study banners stationed here, with high-level details including steps and eligibility criteria (see “Banners”).
- Appropriate distancing markers on the floor to remind study participants to maintain distance while waiting in line
- Welcome Package: bottled water, pens, brochure (see “General Brochure”), and basic study plan (no informed consent form)
- Have alcohol-based hand rub (ABHR) station available to facilitate hand hygiene
- Provide a mask if passenger is not wearing mask
- Check basic inclusion/exclusion criteria
- Answer basic questions about the study
- Inform the risk of denied boarding, if screened positive
- If interested, direct to Informed Consent Area or Citizen Care Pod (5 stations) or wait inside terminal (5 seats allowing physical distancing with dividers)

Citizen Care Pod

- Passenger (potential study subject) will sanitize hands upon entry
- Potential study subject will sit at 1/5 station, facing curb-side side (these 5 stations will have partitions between participants as a physical barrier)
- Clinical Coordinator (all wearing PPE – gown, mask, shield, and gloves, more details below) will come up behind the subject to go through the informed consent
- Once signed consent form, proceed to collect NP swab and oral rinse
- Make sure the subject has no signs of bleeding after NP swab, and rest
- The subject will be given a questionnaire and directed outside of the Care Pod
- Another hand sanitization station will be available for subjects as they exit

Rapid COVID-19 Testing On Site

- For Phase 1, only the NP swab sample will be tested on site using the rapid test device. If the sample is positive, “Positive Screen Test Results” Protocol will be followed (see below). The remaining NP swab sample and oral rinse sample will be transferred back to research laboratory for confirmatory RT-PCR testing.
- For Phase 2, both the NP swab sample and the oral rinse sample will be tested on site using two separate rapid test devices. If either sample is positive, “Positive Screen Test Results” Protocol will be followed (see below). The remaining samples will be transferred back to research laboratory for confirmatory RT-PCR testing.

Results Office

- Results Office – a private room inside the YVR terminal
- Second waiting area will be available outside of Results Office (these 5 stations will have partitions between participants as a physical barrier)
- Subjects will be asked to fill out the questionnaire on paper, using the pens (to be taken home by study participants) received from Welcome Booth
- After 15-20 min, screening results will be available from Study Coordinator
- Questionnaire will be handed back to Study Coordinator (to obtain results)
- Copy of signed consent form given back to subjects
- For WestJet passengers, WestJet will provide subjects with a discount offer for future flights in appreciation of their participation (see “WestJet Promotional Card”). This will be advertised in advance for Phase 2.

Study Team Members – Daily Self-Assessment

- Prior to working on site every day, each Study Team Member will assess for COVID-19 symptoms using the BC COVID-19 Self-Assessment Tool (<https://bc.thrive.health/covid19/en>)
- The Clinical Team Manager will also review WorkSafe BC policies regularly (<https://www.worksafebc.com/en/about-us/covid-19-updates/covid-19-returning-safe-operation>) for updates

Angry Passengers

- The Study Team will be following specific YVR/airline protocol when passengers become upset or irate.
- We will have a daily YVR/airline point of contact person on site to assist the Study Team at all times.
- When a passenger/subject should become upset or irate, our Study Team will inform our YVR/airline point of contact.
- At this point, the YVR/airline staff will work with security and necessary authorities to resolve the situation.

Unclaimed Results

- If a Study Coordinator advises airline staff results have not been collected by the passenger, airline staff can change the status of the passenger's boarding pass/booking so they will be unable to board the flight.
- Terminal pages can be made for the passenger asking them to return to the check-in area.

“Positive Screen Test Results” Protocol

- All subjects who screen positive will be provided with a face mask if they are not wearing one (they do not need a new mask if they already are wearing one)
- Study Coordinator informs subject that they have a “positive” result and contact airline to advise as well.
- Study Coordinator will inform subject on next steps including Study Team + airline contacts
- A new NP swab sample for confirmatory RT-PCR test will be taken by the trained research staff.
- Passenger will be asked to self-isolate and monitor symptoms as per Public Health Guidelines
- Passenger will be provided a brochure with information and resources while waiting for confirmatory test results. The brochure includes public health information, details on rebooking, and frequently asked questions (see “Awaiting Confirmatory Test Results Brochure”).
- Study Coordinator hands over passenger to airline
- Airline agent returns any checked baggage to the passenger and informs on rebooking options
- YVR/airline will coordinate the transportation of the passenger to get home (either private car pickup – curbside level 3 or taxi – YVR will provide voucher)
- Upon receiving the result of the confirmatory test, the passenger will be contacted by clinical team manager
- Airline will be contacted by clinical team manager to be notified of the test result. The passenger travel profile will be updated accordingly

Provision of Test Report for Negative Test Result

- In the event of a negative test result, the Study Coordinator will, upon the subject's request, provide the subject with a printed test report in the format agreed between the parties which will include the following information:
 - Given name and surname of subject;
 - Type of test used;
 - Test result;
 - Date and time of test; and
 - Name and contact information for institute/laboratory that conducted the test.

Personal Protective Equipment

Study coordinators will have the following Personal Protective Equipment or PPE at their disposal for the purposes of the study:

- Surgical Gloves
- ASTM Level 3 Masks
- Face Shield
- Protective Gowns

Coordinators will dispose of PPE as per hospital protocol and re-apply new PPE once they have fully disinfected their work area and their person.

- new PPE does not need to be changed between study participants
- staff can change gowns when contaminated but gloves need to be changed between each study participant.

1. Read protocol: http://www.bccdc.ca/Health-Professionals-Site/Documents/COVID19_MOH_BCCDC_Donning.pdf
2. Hand hygiene: Clean all surfaces of hands and wrists
3. Don gown (cover torso and wrap around back, fasten in back of neck and waist), mask (secure ties at middle of head and neck, fit nose band to your nose and pull bottom down to completely cover chin), eye protection (place goggles or face shield over face and eyes and adjust to fit), and gloves (extend to cover wrist of gown)
4. Collect nasopharyngeal swab and oral rinse samples
5. Doff gloves, hand hygiene
6. Replace gown and/or gloves if visibly soiled or contaminated
7. Repeat hand hygiene

Protocol for Cleaning Subject Testing Area

The consenting and testing area will be taking place inside the Citizen Care Pods which will be placed just outside of the departure terminal doors. Hand sanitizers will be available upon entry and exiting. All frequent touch surfaces (e.g., countertops, chairs, and door knobs) will be disinfected before the subject enters and after the subject exits.

Storage and Disposal of Biohazardous Materials and Samples

All Samples will be kept in a refrigerator located securely in the Citizen Care Pod. Disposable bins with biohazardous bags will also be inside the Citizen Care Pod. This fridge and disposable bins will be carefully monitored at all times. A curtain will be providing additional separation between passengers entering the Care Pod. Please see Care Pod schematic attached. At the end of each day our Study Team will securely transfer the samples in batches (securely tightened samples be packaged in batches into biohazard bags) to the research and clinical labs for validation and confirmatory testing, respectively. No samples will be left on site at the end of the day. Bins with disposables (inside the Care Pod) will be

cleared by YVR maintenance staff on a daily basis, with daily cleaning and disinfecting. Once the validation and clinical testing has been completed in research or clinical labs, the remaining samples will be disposed of or stored as per study protocol.

Data Collection

Subjects who enroll in the study are entered into the secure database. The following data will be collected using the Questionnaire:

- Age
- Sex
- Ethnicity
- PHN (optional)
- Date of enrolment
- Basic overall Medical history
- Lung Disease history
- Symptoms (e.g. fever, cough, shortness of breath, fatigue, pain, etc.)

Withdrawal from Study

Individuals will be withdrawn from the Study in case of any of the following reasons:

- Withdrawal of consent (no reason required)

Independent Ethics Committee or Research Ethics Board

Recruitment for this study will begin only after full approval of the protocol has been obtained from the Research Ethics Board.

Any protocol amendments will undergo the same review and approval process as the original protocol. A protocol amendment may only be implemented after it has been approved by the Research Ethics Board, unless immediate implementation of the change is necessary for subject safety. In this case, the situation must be documented and reported to the Research Ethics Board as soon as possible. Reports on, and reviews of, the Biobank and its progress will be submitted to the Research Ethics Board by the Investigator at intervals stipulated in their guidelines.

Ethics and Good Clinical Practice Compliance

Good Clinical Practice is an international ethical and scientific quality standard for designing, conducting, recording, and reporting studies that involve human subjects.

UBC-YVR-WestJet COVID-19 Screening Study

REB# H20-03225

Version 4.1, Date: 2 Feb 2021

Compliance with this standard provides public assurance that the rights, safety, and well-being of research participants are protected; consistent with the principles that have their origin in the Declaration of Helsinki, and that the research data are credible.

Recruiting Sites

- Onsite at YVR Airport
- Offsite through WestJet digital channels (as outlined above)

REFERENCES

1. Coronavirus Worldometer. available at <https://www.worldometers.info/coronavirus/>.
2. Statistics Canada. Canadian Economic Dashboard and COVID-19. available at <https://www150.statcan.gc.ca/n1/pub/71-607-x/71-607-x2020009-eng.htm>.
3. The Star. Turbulence in Canadian opinion on airlines COVID-19 response, poll says. available at <https://www.thestar.com/news/canada/2020/07/07/turbulence-in-canadian-opinion-on-airlines-covid-19-response-poll-says.html>.

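### Acceptability is a stated objective, but no listed data item measures it, no form follows the result, and no count of passengers approached or declining is described

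*Protocol*

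**What the plan says.** The protocol has two numbered objectives. The second is "To evaluate the acceptability of such screening algorithm and determine the costs of deploying the program" (Objectives). Acceptability is not defined further.

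- **What is collected.** Data Collection introduces its list with "The following data will be collected using the Questionnaire" and names age, sex, ethnicity, an optional health number, enrolment date, general medical history, lung disease history and symptoms. Those who enrol are entered in a database.
- **When it is collected.** The Questionnaire is given out after sampling (Citizen Care Pod) and filled in during the wait. Under Results Office: "Questionnaire will be handed back to Study Coordinator (to obtain results".
- **How passengers are reached.** Under Onsite Recruitment, airline staff mention the study at check-in. Item b says "If the Passenger is interested, they will be directed to the Welcome Booth", and item c says "All passengers meeting the inclusion/exclusion criteria will be approached after checking bags". The Welcome Booth list includes "Check basic inclusion/exclusion criteria". WestJet customers may also receive an email before departure and register online (Advance Recruitment).
- **Incentive.** WestJet passengers get a discount offer. Results Office adds "This will be advertised in advance for Phase 2".
- **Analysis.** Statistical Analysis names simple descriptive statistics and the positivity rate.

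**The concern.** An objective needs something observed that bears on it. Acceptability can be observed by asking participants, or inferred from behaviour, chiefly the share of those offered the test who accept it. The protocol as written describes neither adequately: no listed question for participants and no denominator for uptake.

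Both gaps lie in data collection, which this document fixes. An analysis plan can define how answers and refusals are summarised, but it cannot create them afterwards. Feasibility and acceptability are also much of what a pilot of this kind is for. Finishing 900 enrolments without being able to say whether passengers found the algorithm acceptable would leave part of a named objective largely unanswered.

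**Working it through.** The protocol gives no figure for acceptability to reproduce, so the check compares its sections and uses simple counts.

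**1. Listed data against the objective.** The categories under Data Collection are age, sex, ethnicity, health number, enrolment date, medical history, lung disease history and symptoms. That is 8 categories. Those concerning willingness, burden, discomfort, worry or satisfaction: 0 of 8.

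**2. Timing of the form.** The order is approach and consent, sampling, Questionnaire issued, wait of 15 to 20 minutes, Questionnaire returned, result given.

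| Part of the algorithm | Could a form returned before the result cover it? |
|---|---|
| Approach, consent, NP swab, oral rinse, waiting | Yes |
| View on the risk of denied boarding or a missed flight | Yes: the info sheet and Welcome Booth staff tell passengers beforehand |
| Receiving the result | No |
| For screen positives: hand-over to the airline, rebooking, self-isolation, confirmatory result | No |

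The last row concerns screen positives only. Their number is unknown, because the protocol states no expected positivity. Screen positives are contacted again with the confirmatory result, but no data collection is attached to that contact.

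**3. Can uptake stand in?** Uptake = enrolled / approached.

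- Numerator: known, from signed consent forms and the database. The planned value is a fixed target, 200 (Phase 1) + 700 (Phase 2) = 900.
- Denominator: no count is described at check-in, at the Welcome Booth or after bag check.

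With assumed denominators, for illustration only:

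- 900 / 1,000 = 90%
- 900 / 3,000 = 30%
- 900 / 9,000 = 10%

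The data described are equally compatible with all three, so reaching 900 says nothing about willingness.

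**4. Other behavioural signals.** Online sign-ups cover WestJet advance recruits only. Withdrawals and upset passengers are partial signals. Uncollected results are weak, because of what can follow: "If a Study Coordinator advises airline staff results have not been collected by the passenger", staff may alter the booking so that the passenger cannot board. None of these is named as an acceptability measure.

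**5. Reach of a change now.** The protocol does not say whether Phase 1 is complete. If it is, at most 700 / 900 = 77.8% of subjects can be covered. If it is not, more can be.

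**The case against.** The strongest objection is that the form is not shown. The protocol does not call its list exhaustive, and the list omits the contact details needed to reach screen positives, so the actual form may hold items that the list leaves out. This stands, and it limits confidence. It does not remove the point: if such items exist, the list needs correcting, and a form returned before the result would still miss what comes after it.

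Second, acceptability is undefined, and an analysis plan could build it partly from sign-ups, unclaimed results, complaints and withdrawals. That is fair as far as it goes. Those signals are partial, and they say little about passengers who declined at the airport.

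Third, it is a pilot meant to intrude little on travel, and acceptability is half of the second objective; the stated primary objective is feasibility and effectiveness. This argues for a small remedy, not for none.

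Three stronger readings are tempting, and the documents do not support them:

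- *Consenting passengers go uncounted.* They are counted, through signed forms and the database. Only the denominator is missing.
- *The Questionnaire could not capture any view on denied boarding.* Passengers are warned of that risk beforehand, so their view of it could be asked. Only the experience could not.
- *Every positive-result step falls after the form is returned, so most of the algorithm is missed for all 900.* A positive-result procedure must follow the result by construction, and it applies only to screen positives. For screen negatives, most of the process comes before the form is returned.

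**Conclusion.** The point holds. None of the 8 listed categories covers acceptability, no instrument follows the result, and uptake lacks a described denominator. Followed as written, the protocol leaves the acceptability part of Objective 2 largely unanswerable across a planned 900 enrolments, though not wholly without signals. The positivity estimate is unaffected.

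This rests on two assumptions: that the published list reflects the unseen form, and that no tally is kept in collateral material that is not shown. Confidence is therefore moderate. It should be fixed, since the change is cheap and the loss cannot be repaired after collection.

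**What to change.** 1. Add two or three acceptability items to the existing Questionnaire, for example whether the passenger would use the screening again, how burdensome it was, and worry about missing the flight. Add them to the list under Data Collection.
2. Ask one or two short items when the result is given. Ask screen positives at the contact already planned for the confirmatory result, and report their answers as counts.
3. Keep a simple tally of passengers approached and declining, by airline and phase, and report uptake against it. Count once anyone who is both informed at check-in and approached after bag check. The split by airline matters because the email and discount are for WestJet passengers only; the split by phase, because the discount is advertised ahead in Phase 2.

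**Cost.** An ethics amendment; about one minute per participant (an assumption); and a small extra task for staff already on site. Some passengers will not answer after the result. Answers given before it may be biased, because returning the form is a step to obtaining the result; the report should say so.

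### Does the protocol summarise a rare positivity rate by mean, variance and SD, so that no positives among 200 would look like certainty?

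*Protocol*

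**What the plan says.** Under Research Design, Phase 1, the Protocol sets the size ("We will work with YVR and WestJet to enroll 200 subjects into the study") and the quantity of interest: "For this initial phase we are looking to determine the rate of positivity in the cohort". The next sentence gives the phase its purpose: "This initial phase is needed to evaluate the feasibility of this pilot program and to refine the initial management algorithm". Phase 2 plans "to enroll 700 subjects into the study".

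The Statistical Analysis paragraph consists of one sentence: "When we aggregate the data for analysis, we will use basic statistics to determine mean, variance, standard deviation, and positivity rate...etc".

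The Protocol shown gives no expected positivity, target precision, confidence level or derivation of 200. It names no interval method of any kind. Neither phase has a rule under which a given positivity rate triggers or blocks a next step.

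**The concern.** The study screens departing passengers who are not selected for suspected infection. It also applies the criterion "We will exclude subjects who have previously tested positive for COVID-19 within the past 90 days", and the Protocol says a screening test "has a lower sensitivity (i.e. ability to pick up the virus) than that of a diagnostic test". Few positives among 200 is therefore a reasonable expectation.

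For a yes/no outcome with proportion p, the variance is p(1 − p) and the SD is its square root, so neither adds anything to the rate itself. If no one tests positive, all three are zero. A report of 0% with SD 0 could be taken to mean that there are no infected travellers, when the data would still allow a rate of nearly 2%. Phase 1 precedes the refinement of the algorithm and the choice of throughput strategy for Phase 2, so a misread zero could carry forward. If the plan really tied its uncertainty statement to the SD, this would be a genuine error of method.

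**Working it through.** **1. The planned size.** The Protocol gives no inputs for 200, so the figure can be neither reproduced nor called wrong. A single-proportion precision formula, n = z²p(1 − p)/d², comes close only with arbitrary choices: p = 5% and d = 3 points gives 203; p = 50% and d = 7 points gives 196. None of these is stated.

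**2. What 200 subjects can show.** Inputs: n = 200 from Research Design, and an assumed two-sided 95% level.

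- Exact (Clopper-Pearson) upper limit at 0/n: 1 − 0.025^(1/n). For n = 200 this is 1.83%. The Wilson upper limit is 1.88%.
- Normal (Wald) interval: p ± 1.96 × √(p(1 − p)/n).

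| Positives | Rate | SD | Wald 95% interval | Exact 95% interval |
|---|---|---|---|---|
| 0/200 | 0% | 0 | 0 to 0 | 0 to 1.83% |
| 1/200 | 0.5% | 0.071 | −0.48% to 1.48% | 0.01% to 2.75% |
| 2/200 | 1.0% | 0.099 | −0.38% to 2.38% | 0.12% to 3.57% |

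The collapse at zero and the negative lower limits are correct as arithmetic.

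**3. Is zero positives likely?** The expected rate is not in the document, so it is assumed over a range. P(0 of 200) = (1 − p)^200:

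| Assumed test positivity | 0.1% | 0.2% | 0.3% | 0.5% | 1% | 2% |
|---|---|---|---|---|---|---|
| P(0 of 200) | 82% | 67% | 55% | 37% | 13% | 1.8% |

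The chance reaches 50% at p = 1 − 0.5^(1/200) = 0.35%. Zero is the more likely outcome only below that rate. The p here must be the rate of positive tests, which includes false positives, and not the prevalence of infection. No specificity is given. If it were 99.5% (an assumption), the chance of no false positive among 200 uninfected people would be 0.995^200 = 37%, before any true positive is counted.

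**4. Does the plan apply these summaries to positivity?** The Statistical Analysis sentence has four named items followed by an open end. Positivity rate is the fourth, set beside mean, variance and SD and not described by them. The study also has quantities for which mean and SD are natural: age is recorded under Data Collection, and the cost of deployment is part of the second objective. The ordinary reading is mean and SD for such items and a rate for test positivity. Nothing in the text says otherwise, and no Wald or other SD-based interval appears anywhere. The negative limits in step 2 therefore belong to a method the plan does not propose.

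**5. Is the aim beyond reach?** The aim is the rate in the cohort. For the 200 people enrolled, that is a count over a denominator, and testing them determines it. A claim about travellers in general would need an interval, but the Protocol makes no such claim and sets no precision that 200 would miss.

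**The case for a change.** The strongest case for keeping the concern does not need zero to be the likeliest result. An SD-based interval falls below zero for 1, 2 or 3 positives as well (at 3/200 it is −0.18% to 3.18%) and first stays above zero at 4/200. The chance of 3 or fewer positives is above 99% at 0.1% positivity, 98% at 0.5%, 86% at 1% and still 43% at 2%. Positivity is the only quantity that Phase 1 is said to estimate, and variance and SD are the only measures of spread the Protocol names. And whatever an analysis plan adds, 0/200 can only bound a population rate at 1.83%, so the word determine promises too much.

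The numbers stand, and so does the observation that the Protocol names no interval and ties 200 to no precision. The rest does not follow. The wider range of bad outcomes is bad only for an interval nobody proposes. A sample SD describes data and is not offered as a measure of uncertainty about the rate. The missing interval method is a detail that commonly belongs in an analysis plan, which may exist but is not shown. Preferring bound to determine is a choice of words that changes no result and no decision.

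The feared consequence is also not documented. The Protocol links Phase 1 to feasibility and to refining the algorithm, but does not say that the positivity estimate drives either, or the throughput strategy. Its own account of screening tests says that people with a negative screen must still be treated as possibly infectious, which works against reading a zero as absence of infection.

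**Conclusion.** The concern does not hold. The Protocol lists the positivity rate as a summary in its own right and nowhere says it will be expressed through a mean, variance or SD. The gap between 0% with SD 0 and an exact upper limit of 1.83% is real arithmetic, but it describes an analysis the plan does not state. What is left is that no interval method is named, and that is no finding while the analysis plan is not shown.

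This rests on two readings of the text: that positivity rate is separate from the three items before it, and that the Phase 1 aim concerns the enrolled cohort of a pilot. It does not depend on any assumed prevalence. The range in step 3 shows only that zero positives cannot be called likely from this document. The conclusion would change if an analysis plan specified an SD-based or normal interval for the positivity rate, or attached a decision rule to the Phase 1 estimate.
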